5.0 Study Design*

- 5.1 Describe and explain the study design (e.g. case-control, cross-sectional, ethnographic, experimental, interventional, longitudinal, observational).

Response:

It will be a cross sectional study with 2 groups of patients.

University at Buffalo Institutional Review Board (UBIRB)

Office of Research Compliance | Clinical and Translational Research Center Room 5018
[name]
UB Federalwide Assurance ID#: FWA00008824

One group will be men with prostate cancer in various stages of ADT and the control group will be men with prostate cancer not on ADT.

6.0 Study Intervention/Investigational Agent

6.1 *Describe the study intervention and/or investigational agent (e.g., drug, device) that is being evaluated.*

Response:

NA

6.2 *Drug/Device Handling: If the research involves drugs or device, describe your plans to store, handle, and administer those drugs or devices so that they will be used only on subjects and be used only by authorized investigators.*

- *If the control of the drugs or devices used in this protocol will be accomplished by following an established, approved organizational SOP (e.g., Research Pharmacy SOP for the Control of Investigational Drugs, etc.), please reference that SOP in this section.*

Response:

NA

6.3 *If the drug is investigational (has an IND) or the device has an IDE or a claim of abbreviated IDE (non-significant risk device), include the following information:*

- *Identify the holder of the IND/IDE/Abbreviated IDE.*
- *Explain procedures followed to comply with sponsor requirements for FDA regulated research for the following:*

FDA Regulation	Applicable to:		
	IND Studies	IDE studies	Abbreviated IDE studies
21 CFR 11	X	X	
21 CFR 54	X	X	
21 CFR 210	X		
21 CFR 211	X		
21 CFR 312	X		
21 CFR 812		X	X
21 CFR 820		X	

Response:

University at Buffalo Institutional Review Board (UBIRB)

Office of Research Compliance | Clinical and Translational Research Center Room 5018
[name]
UB Federalwide Assurance ID#: FWA00008824

7.0 Local Number of Subjects

7.1 *Indicate the total number of subjects that will be enrolled or records that will be reviewed locally.*

Response:

40

7.2 *If applicable, indicate how many subjects you expect to screen to reach your target sample (i.e. your screen failure rate).*

Response:

We expect to screen 130 to 150 patients

7.3 *Justify the feasibility of recruiting the proposed number of eligible subjects within the anticipated recruitment period. For example, how many potential subjects do you have access to? What percentage of those potential subjects do you need to recruit?*

Response:

Preliminary assessment suggests up to 20 patients per month begin treatment with ADT in the GU oncology clinic. We anticipate that a majority (10) will be eligible and 30% (3) will agree to participate in the trial.

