8.0 Inclusion and Exclusion Criteria*

8.1 *Describe the criteria that define who will be **included** in your final study sample.*

NOTE: This may be done in bullet point fashion.

Response:

1. Male, age \geq 18 years of age.
2. Body Mass Index of $> 25 \text{ kg/m}^2$
3. Biopsy-confirmed prostate adenocarcinoma of any stage/grade currently on androgen deprivation therapy (ADT) for minimum of 3 months
4. Biopsy-confirmed prostate adenocarcinoma of any stage/grade not on ADT for control group
5. Hemoglobin $> 11 \text{ g/dL}$, Creatinine $< 1.5 \times \text{ULN}$ and liver function tests $< 2 \times \text{ULN}$
6. Participant must be able to read, write, and understand the English language and be able to provide written consent

University at Buffalo Institutional Review Board (UBIRB)

Office of Research Compliance | Clinical and Translational Research Center Room 5018
[name]
UB Federalwide Assurance ID#: FWA00008824

7. Participant must understand the investigational nature of this study and sign an Independent Ethics Committee/Institutional Review Board approved written informed consent form prior to receiving any study related procedure

8.2 Describe the criteria that define who will be *excluded* from your final study sample.

NOTE: This may be done in bullet point fashion.

Response:

1. Known clinically significant severe COPD, ischemic heart disease, congestive heart failure, and/or significant cardiac arrhythmias
2. Any patient with known diabetes (A1c > 6.4%) or an anti-diabetic drug
3. Any condition contraindicating additional blood collection beyond standard of care
4. Subjects with known allergy to lidocaine (this is used to anesthetize area for fat biopsy)
5. Unwilling or unable to follow protocol requirements
6. Any condition which in the Investigator's opinion deems the participant an unsuitable candidate to undergo study procedures.
7. Subjects on chronic use of androgens, or opiates in the last 6 months or with panhypopituitarism, congenital HH (hypogonadotropic hypogonadism), prolactinoma, head trauma

8.3 Indicate specifically whether you will include any of the following special populations in your study using the checkboxes below.

NOTE: Members of special populations may not be targeted for enrollment in your study unless you indicate this in your inclusion criteria.

Response: NA

- Adults unable to consent
- Individuals who are not yet adults (infants, children, teenagers)
- Pregnant women
- Prisoners

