11.0 Recruitment Methods

N/A: This is a record review only, and subjects will not be recruited.
NOTE: If you select this option, please make sure that all records review procedures and inclusion/exclusion screening are adequately described in other sections.

11.1 *Describe when, where, and how potential subjects will be recruited.*

NOTE: Recruitment refers to how you are identifying potential participants and introducing them to the study. Include specific methods you will use (e.g. searching charts for specific ICD code numbers, Research Participant Groups, posted advertisements, etc.).

Response:

Study participants will be recruited from the RPCCC (Roswell Park Comprehensive Cancer Center) GU Oncology clinical program (Hematology and Oncology, Urology, and Radiation Oncology), Prostate Cancer Survivorship group and Biodata Repository (BDR) and Great Lakes Cancer Care GU clinics by the attending physicians. Patient records will be reviewed at the time of clinical encounter as well as from the BDR to identify potentially eligible individuals. If a participant is identified during clinical encounter, physicians will speak to them about their interests in participating in research. If a participant is identified from the BDR, they will be contacted through phone by the GU team (members listed in the study) about their interests in participating in research. The GU team will refer the interested participants to the Diabetes and Endocrinology Research Center of Western New York where they will be screened and consented

11.2 *Describe how you will protect the privacy interests of prospective subjects during the recruitment process.*

NOTE: Privacy refers to an individual's right to control access to him or herself.

Response:

University at Buffalo Institutional Review Board (UBIRB)

Office of Research Compliance | Clinical and Translational Research Center Room 5018
[name]
UB Federalwide Assurance ID#: FWA00008824

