19.0 Data Management and Analysis*

19.1 Describe the data analysis plan, including any statistical procedures. This section applies to both quantitative and qualitative analysis.

Response:

The demographic features of the population and screening lab results will be displayed in tables. Statistical analysis will be carried out using SPSS and SigmaStat software (SPSS, IL). All data will be expressed as mean \pm S.E of arbitrary units and percent change is calculated from the means. To evaluate similarity between the study groups, baseline values for subject's demographics will be compared using appropriate parametric and non-parametric tests based upon the nature of the data

19.2 If applicable, provide a power analysis.

NOTE: This may not apply to certain types of studies, including chart/records reviews, survey studies, or observational studies. This question is asked to elicit whether the investigator has an adequate sample size to achieve the study objectives and justify a conclusion.

Response:

Based on our previous study, HH men have greater insulin resistance by 30% compared to eugonadal men. Therefore, a sample size of 20 patients in each group is sufficient to provide adequate power (80%) to detect a significant difference ($p<0.05$) in insulin resistance of $\geq 30\%$ between patients with ADT (negligible testosterone) and non-ATD patients (low to normal testosterone) assuming the standard deviation of the difference is $\leq 30\%$. and a drop-out rate of about 15%.

19.3 Describe any procedures that will be used for quality control of collected data.

University at Buffalo Institutional Review Board (UBIRB)

Office of Research Compliance | Clinical and Translational Research Center Room 5018
[name]
UB Federalwide Assurance ID#: FWA00008824

Response:

Three investigators and research nurse will double check the accuracy of collected data. All laboratory testing will be standardized using references and standards.

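### Does a stated accrual of 3 men a month, at most 18 in 6 months, undermine a plan to enrol 40?

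*Combined protocol and SAP*

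**What the plan says.** Sections 7.1 and 19.2 plan 40 men, 20 on ADT and 20 not. Section 7.2 states: "We expect to screen 130 to 150 patients". The form then asks for evidence that the target can be reached in the recruitment period, and section 7.3 answers with one flow: "Preliminary assessment suggests up to 20 patients per month begin treatment with ADT in the GU oncology clinic", followed by "We anticipate that a majority (10) will be eligible and 30% (3) will agree to participate in the trial".

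Four other places bear on this:

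- Section 8.1, item 3 admits a man to the ADT group only if he is "currently on androgen deprivation therapy (ADT) for minimum of 3 months". Item 4 requires controls to be off ADT.
- Section 11.1 recruits from the cancer centre's genitourinary oncology programme and also from the "Prostate Cancer Survivorship group and Biodata Repository (BDR) and Great Lakes Cancer Care GU clinics by the attending physicians". It gives no numbers for these sources.
- Section 13.1 anticipates 6 months to enrol everyone, and section 13.3 estimates 12 months to finish the study, analysis included.
- Section 13.2 gives each man's participation as up to 7 days.

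**The concern.** The passage meant to show feasibility seems to show the reverse. Its rate yields 18 men in the enrolment period: fewer than the 20 for the ADT group and less than half of the 40. It counts men on the day they begin ADT, when none of them yet meets the 3-month minimum. The controls, who are half the study, have no rate at all.

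Two things could be at stake. If enrolment stopped at 6 months, the comparison would rest on fewer men than the power statement assumes. If enrolment continued, the 6 and 12 months in sections 13.1 and 13.3 would be too short.

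**Working it through.** **1. The plan's own rate.** Inputs from section 7.3: up to 20 starters a month, 10 eligible, 30% agreeing. 10 × 0.30 = 3 a month, as stated.

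**2. Yield in the enrolment period (13.1).** 3 × 6 = 18. This is a ceiling, because 20 starters is given as an upper limit.

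**3. Against the targets.**

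| Reading of the rate | Target | Shortfall in 6 months | Months needed at 3 a month |
|---|---|---|---|
| ADT group only | 20 | 20 − 18 = 2 | 20/3 = 6.7 |
| Whole study | 40 | 40 − 18 = 22 | 40/3 = 13.3 |

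The first row is the natural reading. Section 7.3 counts men starting ADT in one clinic, controls are by definition off ADT, and section 11.1 lists further sources. The second row, with its 13.3 months against the 12 of section 13.3, requires the rate to mean something the section does not say.

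**4. How firm is the 18?** The text calls 10 of 20 a majority, although 10/20 is exactly half. With 11 eligible, the smallest true majority, 11 × 0.30 × 6 = 19.8, which is practically the 20 planned. A gap of 2 lies within the precision of the inputs.

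**5. The 3-month minimum.** If only men who start ADT after the study opens could enter, accrual would run for 6 − 3 = 3 months and give 3 × 3 = 9 men. That restriction is not in the protocol. Men who started in the 3 months before opening reach the minimum during the first 3 months, so with steady starts the monthly flow remains about 3. Men on ADT for longer come on top of this: section 4.1 notes that treatment may last for years, and section 5.1 recruits men at various stages of ADT.

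**6. The number screened.** 0.30 × 130 = 39 and 0.30 × 150 = 45, so section 7.2 fits a target of 40 if it counts eligible men approached. The clinic flow supplies 10 × 6 = 60 such men, which would leave 130 − 60 = 70 to 150 − 60 = 90 for other sources. However, section 10.1 describes screening as consent, history, examination and blood tests, while sections 11.1 and 11.2 describe review of charts before any approach. The protocol does not say which of these section 7.2 counts, so the 70 to 90 is not an established deficit.

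**7. Power if the ADT group did close at 18.** Assumptions: two-sided 5% t-test, 30% difference, and the 30% SD of section 19.2 taken as the within-group SD, so d = 30/30 = 1. The t-test needs 16.7, so 17 per group; 17/0.85 = 20 allows for 15% dropout and reproduces the plan's figure. Power is 0.807 at 17 v 17. With 18 and 20 enrolled, dropout leaves 18 × 0.85 = 15.3 (15) and 20 × 0.85 = 17, with power 0.780. The cost is under 3 percentage points.

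**8. Does anything depend on the 6 months?** Section 13.1 is an anticipated duration, and no section closes enrolment on a date. The endpoint review in section 21.7 is triggered when half of the recruited men have completed, not at a calendar time. Each man is measured once, within up to 7 days, so slower accrual truncates nobody's follow-up.

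**The case for a change.** The best case for a change is that the form asks how many potential subjects are available, and for half the study the protocol gives no answer. This does not depend on how the rate is read. Beyond the clinic's 18, the uncounted sources must provide 22 men (2 on ADT and 20 controls) in 6 months. At 30% agreement that is 22/0.30 = 73 eligible men approached, about 12 a month, more than the 10 a month the clinic itself is said to supply. Participants undergo a fat biopsy and a research-only DEXA scan without direct benefit, so an ethics board may reasonably want evidence that both groups can be filled.

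Part of this stands. Section 7.3 is incomplete as a feasibility statement, and the missing control count is its clearest gap. The 73 is weaker, because 30% is stated only for ADT starters. At half that rate the figure is 22/0.15 = 147 men, about 24 a month; at double it is 22/0.60 = 37 men, about 6 a month. The sizes of the survivorship group, the repository and the second clinic network are not given, so none of these figures can be called out of reach. Incomplete evidence for 6 months does not show that 6 months is wrong.

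**Conclusion.** No change to the plan follows. This is missing detail in a feasibility answer, and supplying it would not alter any result. The arithmetic is right: the only stated rate gives at most 18 men in 6 months, it counts men at the start of ADT, and it does not cover controls. On the natural reading the ADT group is 2 men, or 0.7 month, short on a preliminary estimate, and named but uncounted sources can supply those men and the controls.

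If accrual proves slow, the study runs past its anticipated dates and reaches the same 20 per group, with the same endpoints and analysis. Even if the ADT group closed at 18, power after dropout would be 0.780 rather than 0.807 under the plan's own effect and SD.

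The conclusion rests on three assumptions: the rate in section 7.3 refers to ADT starters only; men who began ADT before the study opened may enter, which section 8.1 allows; and enrolment may continue beyond 6 months, which nothing in the protocol prevents. The documents cannot settle whether enough controls exist at the named sources. That is a question for recruitment monitoring, and section 16.2 already puts the recruitment rate on the agenda of weekly research meetings.

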8.0 Inclusion and Exclusion Criteria*

8.1 *Describe the criteria that define who will be **included** in your final study sample.*

NOTE: This may be done in bullet point fashion.

Response:

1. Male, age \geq 18 years of age.
2. Body Mass Index of $> 25 \text{ kg/m}^2$
3. Biopsy-confirmed prostate adenocarcinoma of any stage/grade currently on androgen deprivation therapy (ADT) for minimum of 3 months
4. Biopsy-confirmed prostate adenocarcinoma of any stage/grade not on ADT for control group
5. Hemoglobin $> 11 \text{ g/dL}$, Creatinine $< 1.5 \times \text{ULN}$ and liver function tests $< 2 \times \text{ULN}$
6. Participant must be able to read, write, and understand the English language and be able to provide written consent

University at Buffalo Institutional Review Board (UBIRB)

Office of Research Compliance | Clinical and Translational Research Center Room 5018
[name]
UB Federalwide Assurance ID#: FWA00008824

7. Participant must understand the investigational nature of this study and sign an Independent Ethics Committee/Institutional Review Board approved written informed consent form prior to receiving any study related procedure

8.2 Describe the criteria that define who will be *excluded* from your final study sample.

NOTE: This may be done in bullet point fashion.

Response:

1. Known clinically significant severe COPD, ischemic heart disease, congestive heart failure, and/or significant cardiac arrhythmias
2. Any patient with known diabetes (A1c > 6.4%) or an anti-diabetic drug
3. Any condition contraindicating additional blood collection beyond standard of care
4. Subjects with known allergy to lidocaine (this is used to anesthetize area for fat biopsy)
5. Unwilling or unable to follow protocol requirements
6. Any condition which in the Investigator's opinion deems the participant an unsuitable candidate to undergo study procedures.
7. Subjects on chronic use of androgens, or opiates in the last 6 months or with panhypopituitarism, congenital HH (hypogonadotropic hypogonadism), prolactinoma, head trauma

8.3 Indicate specifically whether you will include any of the following special populations in your study using the checkboxes below.

NOTE: Members of special populations may not be targeted for enrollment in your study unless you indicate this in your inclusion criteria.

Response: NA

- Adults unable to consent
- Individuals who are not yet adults (infants, children, teenagers)
- Pregnant women
- Prisoners

8.4 Indicate whether you will include non-English speaking individuals in your study. Provide justification if you will exclude non-English speaking individuals.

University at Buffalo Institutional Review Board (UBIRB)

Office of Research Compliance | Clinical and Translational Research Center Room 5018
[name]
UB Federalwide Assurance ID#: FWA00008824

*In order to meet one of the primary ethical principles of equitable selection of subjects, non-English speaking individuals may **not** be routinely excluded from research as a matter of convenience.*

In cases where the research is of therapeutic intent or is designed to investigate areas that would necessarily require certain populations who may not speak English, the researcher is required to make efforts to recruit and include non-English speaking individuals. However, there are studies in which it would be reasonable to limit subjects to those who speak English. Some examples include pilot studies, small unfunded studies with validated instruments not available in other languages, studies with numerous questionnaires, and some non-therapeutic studies which offer no direct benefit.

Response:

We will not have non-English speaking individuals in this study. We have patients that English is a second language, but they are able to read, write and understand it. This population is less than 10% of the total population

We are excluding non-English speaking individuals as this is a small study and no benefits will be withheld.

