2.0 Objectives*

2.1 Describe the purpose, specific aims, or objectives of this research.

Response:

PRIMARY OBJECTIVE

To investigate the possible cellular and molecular mechanisms underlying or associated with insulin resistance in patients undergoing androgen deprivation therapy for prostatic carcinoma including determining the expression of insulin signaling genes and proinflammatory genes associated with insulin resistance.

SECONDARY OBJECTIVES

1. Determine level of insulin resistance at different stages of ADT treatment compared to those not on ADT
2. Correlate level of insulin resistance to the expression of insulin signaling genes and inflammatory mediators associated with insulin resistance
3. Determine the effect of insulin resistance on body composition of men undergoing ADT.
4. Determine cognitive function scores in patients receiving ADT at various stages.

2.2 State the hypotheses to be tested, if applicable.

NOTE: A hypothesis is a specific, testable prediction about what you expect to happen in your study that corresponds with your above listed objectives.

Response:

We hypothesize that ADT results in increase in insulin resistance and in inflammatory mediators which may interfere with insulin signal transduction. We hypothesize that ADT results in greater adiposity and an increase in plasma insulin and glucose concentrations with a concomitant increase in HOMA-IR, plasma TNF α and IL-1 β with a decrease in the expression of IR β , IRS-1, AKT and GLUT-4 in adipose tissue

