4.0 Background*

University at Buffalo Institutional Review Board (UBIRB)

Office of Research Compliance | Clinical and Translational Research Center Room 5018
[name]
UB Federalwide Assurance ID#: FWA00008824

4.1 Provide the scientific or scholarly background, rationale, and significance of the research based on the existing literature and how it will contribute to existing knowledge. Describe any gaps in current knowledge. Include relevant preliminary findings or prior research by the investigator.

Response:

Prostate cancer (PrCa) is the most common non-cutaneous malignancy amongst men in the United States. Early stage, organ-confined PrCa can be cured by surgery or radiotherapy. While the majority of men are diagnosed with early stage disease, many present with more advanced disease or are otherwise not good candidates for curative therapies. In addition, one third of patients with localized disease will eventually develop metastatic PrCa. The mainstay treatment of locally advanced, as well as recurrent or metastatic PrCa is androgen deprivation therapy (ADT)^[1], which blocks the production of male hormones and induces tumor cell apoptosis^[2].

ADT either via castration or more frequently, gonadotropin-releasing hormone (GnRH) agonists (such as leuprolide), reduces serum testosterone (T) to castrate levels^[3]. Despite initial responses, almost all patients will eventually develop disease progression, which in the presence of continuous ADT is defined as castration resistant PrCa (CRPC). Some CRPC patients may respond for a number of years to sequential administration of more potent anti-androgens combined with ongoing continuous ADT^[4]. Thus, it is not unusual for men with advanced PrCa to be on continuous ADT for many years.

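### Disease state differs between the ADT and control groups by the way they are defined, and the plan neither names it for collection nor handles it in the analysis, so any effect of advancing cancer would be credited to ADT

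*Combined protocol and SAP*

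**What the plan says.** Section 5.1 sets up two groups of men with prostate cancer: one at differing points in a course of ADT, and a control group that is not receiving it. Section 8.1 defines them by treatment and leaves disease extent open on both sides. Item 3, for the ADT group, asks for "Biopsy-confirmed prostate adenocarcinoma of any stage/grade currently on androgen deprivation therapy (ADT) for minimum of 3 months". Item 4, for controls, asks for "Biopsy-confirmed prostate adenocarcinoma of any stage/grade not on ADT for control group". Section 8.2 has no exclusion for metastatic or castration-resistant disease, and matching is not mentioned.

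Section 4.1 says who receives ADT: "The mainstay treatment of locally advanced, as well as recurrent or metastatic PrCa is androgen deprivation therapy (ADT"). It describes later progression, "which in the presence of continuous ADT is defined as castration resistant PrCa (CRPC"), and adds: "Thus, it is not unusual for men with advanced PrCa to be on continuous ADT for many years".

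The hypothesis in section 2.2 is causal: "We hypothesize that ADT results in increase in insulin resistance and in inflammatory mediators which may interfere with insulin signal transduction". Section 3.1 makes expression of proinflammatory genes a primary endpoint. HOMA-IR, plasma inflammatory markers and body composition are secondary.

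Section 19.1 compares the groups on demographics. It names no covariate, stratification, restriction or sensitivity analysis for disease state. Section 12.2, on data to be collected, does not mention stage, metastatic status, PSA or castration resistance. Section 12.1 does include a medical history, and section 12.4 lists electronic records and clinical charts as sources.

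**The concern.** Admitting any stage to both groups looks even-handed, but it does not make the groups alike. The reason a man is on ADT is the state of his cancer, so a comparison by ADT status is also partly a comparison by disease state. This is confounding by indication. One state, castration resistance, has no possible counterpart among controls.

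The study asks whether ADT raises inflammatory mediators and insulin resistance. If advancing cancer itself moves those markers, or body composition, the planned contrast adds that movement to any ADT effect and labels the sum as ADT. Without disease state in the dataset and the analysis, a reader of the results could not judge how much of a difference to discount.

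**Working it through.** **Step 1: what the text fixes.** Three statements side by side:

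- ADT is given mainly for locally advanced, recurrent or metastatic disease (4.1).
- Castration resistance requires progression while on continuous ADT (4.1).
- Controls are not on ADT (5.1; 8.1 item 4).

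The last two mean that the share of controls with castration-resistant disease is zero by definition. The first makes metastatic disease likely to be more common in the ADT group, but gives no proportions.

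**Step 2: the plan's own sample size.** Section 19.2 gives a 30% difference, an SD of at most 30%, p<0.05, 80% power and about 15% dropout. I take the test as two-sided and the SD as the within-group SD. The standardised difference is 30/30 = 1.0. The two-sample t-test needs 16.7, so 17 evaluable men per group, and 17/0.85 = 20. This reproduces the stated 20 per group, and power at 17 per group is 80.7%. The sample size is not at fault here, and 17 per group is used below.

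**Step 3: size of a spurious contrast.** Let pA and pC be the shares of ADT men and controls with advanced (metastatic or castration-resistant) disease. Let d be the shift in a marker, in SD units, that such disease causes. With no ADT effect, the expected group difference is

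Δ = d × (pA − pC).

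The documents give none of these three quantities. I assume pA of 30% to 60%, pC of 0% or 10%, and d of 0.5 or 1.0. The last two columns are simulated rejection rates for an unadjusted two-sided 5% t-test with 17 per group.

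| pA | d (SD) | Δ at pC = 0 | Δ at pC = 10% | Rejects, pC = 0 | Rejects, pC = 10% |
|---|---|---|---|---|---|
| 30% | 0.5 | 0.15 | 0.10 | 7% | 6% |
| 30% | 1.0 | 0.30 | 0.20 | 13% | 8% |
| 50% | 0.5 | 0.25 | 0.20 | 11% | 9% |
| 50% | 1.0 | 0.50 | 0.40 | 27% | 18% |
| 60% | 0.5 | 0.30 | 0.25 | 13% | 11% |
| 60% | 1.0 | 0.60 | 0.50 | 36–37% | 26% |

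For example, with pA = 50%, pC = 0 and d = 1.0, Δ = 1.0 × 0.5 = 0.5 SD. On the protocol's 30% SD for insulin resistance that is 0.5 × 30 = 15 percentage points, half of the difference the study is designed to detect.

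**Step 4: what a restricted contrast costs.** If leaving out advanced disease reduces the ADT group from 17 to 10 men and all 17 controls stay, power for a 1 SD difference falls from 80.7% to 67.4%. The 95% confidence half-width, t × √(1/n₁ + 1/n₂) in SD units, goes from 2.037 × √(1/17 + 1/17) = 0.70 to 2.060 × √(1/10 + 1/17) = 0.82. Dropping controls as well lowers precision further.

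Covariate adjustment does not escape this cost. If no control has advanced disease, a model with a disease-state term estimates the ADT effect by comparing the non-advanced ADT men with the controls, which is the restricted contrast.

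**The case against.** The strongest reply is that the harm is assumed. No section says that advancing prostate cancer raises these markers or changes insulin resistance, and the prevalences and shifts in the table are not from the documents. At the low end the rejection rate is 6% to 7%, barely above the nominal 5%. This stands: the documents support the structure of the problem but not its size.

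Eligibility also filters some of the sickest men. Section 8.1 requires hemoglobin above 11 g/dL and sets creatinine and liver-test limits; section 8.2 excludes chronic opiate use and allows exclusion at the investigator's discretion. These criteria may lower both the share of advanced disease and its effect on markers. They do not exclude metastatic or castration-resistant men, and they do not balance the groups.

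A reader might infer that the analyst could neither see nor remove the imbalance. The documents do not support that. History is taken, charts are reviewed and listed as a source, and section 12.3 refers to visit forms that are not part of the document. Section 12.2 is mostly an assay list; it also omits height and weight, which section 21.2 says are monitored. The defensible statement is that disease state is not named for collection or for analysis.

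A reader might also infer that metastatic men will sit almost entirely in the ADT group. Section 4.1 names locally advanced and recurrent disease as well, and item 4 admits controls of any stage. Complete separation is established only for castration resistance.

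Finally, admitting any stage serves generalisability, and every cross-sectional comparison carries some confounding. Both are true. Neither is a reason to leave the leading candidate confounder out of the analysis.

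**Conclusion.** The concern holds in conditional form. As the groups are defined, disease state goes with ADT status: castration resistance is confined to the ADT group by definition, and metastatic disease is likely to be more common there. The plan tests a causal ADT hypothesis and checks comparability on demographics only, so whatever effect advancing cancer has on the markers would be credited to ADT.

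The documents do not show that this bias is large, or that it will produce a false finding. Under the stated assumptions the false rejection rate is about 6% to 37% against a nominal 5%, and the eligibility filters may lower it. The structure is certain and the size is unknown. Because the primary attribution is affected and the remedy is cheap, the plan should be changed.

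**What to change.** Add to sections 12.2 and 19.1:

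1. For every man, abstract stage, metastatic status, castration resistance and latest PSA from the clinical charts, and tabulate them by group.
2. Pre-specify that each main ADT versus control contrast is repeated with metastatic and castration-resistant men left out of both groups. Report both estimates with confidence intervals.
3. State that attribution to ADT will be limited if the restricted estimate is materially smaller, and say beforehand what reduction counts as material. With a half-width near 0.8 SD this is a judgement on estimates, not a test.
4. State that an imbalance between locally advanced and localised disease may remain.

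The cost is a short abstraction for 40 men from a source that section 12.4 already lists, some protocol wording and one extra analysis. The downside is precision: power for a 1 SD difference falls from 81% at 17 v 17 to 67% at 10 v 17, and further if controls are also dropped. The any-stage eligibility can stay.

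Optionally, some controls could be men not yet on ADT, since they share its indication. This should not be part of the required change. Section 7.3 reports "up to 20 patients per month begin treatment with ADT in the GU oncology clinic", of whom 10 are expected to be eligible and 3 to consent. Over the 6 months of enrolment in section 13.1 that is 3 × 6 = 18 men, the only pool quantified for all 40 places. Some of these men would be metastatic and would drop out of the restricted contrast.
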